9.2 Serious Adverse Events

A Serious Adverse Event (SAE) will be define as any adverse event that results in any of the following outcomes:

- Death

- Life–threatening adverse experience
- Inpatient hospitalization or prolongation of existing hospitalization
- Persistent or significant disability/incapacity
- Congenital malformation/birth defect
- Any other experience that suggests a significant hazard, contraindication, side effect or precaution that may require medical or surgical intervention to prevent one of the outcomes listed above
- Event that changes the risk/benefit ratio of the study

9.3 Analytical Methods

We will test the hypothesis that pregnant women who receive IPTp with either 3 dose DP or monthly DP will have a lower incidence of adverse events and better tolerability compared to those who receive 3 doses of SP. A modified intention–to–treat approach to all will be used, including all study participants who received at least one dose of study drugs, regardless of whether subsequently the intervention was not given for any reason. We will compare the proportions of study participants with vomiting following each dose of study drugs using generalized estimating equations with a log–binomial family and robust standard errors to account for repeated measures in the same study participant. We will compare the incidence of various adverse events using Poisson or negative binomial regression models. The Poisson models will include the logarithm of the follow–up time as an offset. We will translate the fitted coefficients and their confidence bounds into percentage effects with the formula $100 \times [\exp(\text{coefficient}) - 1]$. This approach is closely related to exponential survival models for analyzing events per follow–up time, but is better able to adjust for violated assumptions. Testing for overdispersion in the Poisson regression can detect violations of these assumptions, and variances can be adjusted accordingly to produce valid p–values and confidence interval. If significant deviations from required distributions in study data are detected, we will employ negative–binomial or zero–inflated negative–binomial models to account for the observed pattern of data. Comparisons of incidence measures will be expressed at the incidence rate ratio (IRR) or the protective efficacy ($PE = 1 - IRR \times 100\%$). A skeleton table for the presentation of safety and tolerability outcomes are presented in Tables 13 below.

Table 13. Measures of safety and tolerability

Outcome	Treatment arm						
	3 dose SP ^a		3 dose DP		Monthly DP		
Prevalence measures	Prevalence	Prevalence	RR (95% CI)	p-value	Prevalence	RR (95% CI)	p-value
Vomiting following administration of study drugs							
Observed after administration of 1 st dose in clinic	n/N (%)	n/N (%)			n/N (%)		
Reported after administration of 2 nd dose at home	n/N (%)	n/N (%)			n/N (%)		
Reported after administration of 3 rd dose at home	n/N (%)	n/N (%)			n/N (%)		
Incidence measures	Events ^b	Events ^b	IRR (95% CI)	p-value	Events ^b	IRR (95% CI)	p-value
Individual adverse events of any severity ^c							
XXXX	xx (x.xx)	xx (x.xx)			xx (x.xx)		
XXXX	xx (x.xx)	xx (x.xx)			xx (x.xx)		
XXXX	xx (x.xx)	xx (x.xx)			xx (x.xx)		
XXXX	xx (x.xx)	xx (x.xx)			xx (x.xx)		
XXXX	xx (x.xx)	xx (x.xx)			xx (x.xx)		
Individual grade 3–4 adverse events ^c							
XXXX	xx (x.xx)	xx (x.xx)			xx (x.xx)		
XXXX	xx (x.xx)	xx (x.xx)			xx (x.xx)		
XXXX	xx (x.xx)	xx (x.xx)			xx (x.xx)		
XXXX	xx (x.xx)	xx (x.xx)			xx (x.xx)		
XXXX	xx (x.xx)	xx (x.xx)			xx (x.xx)		
All grade 3–4 adverse events	xx (x.xx)	xx (x.xx)			xx (x.xx)		
Grade 3–4 adverse events possibly related to stud drugs	xx (x.xx)	xx (x.xx)			xx (x.xx)		
All serious adverse events	xx (x.xx)	xx (x.xx)			xx (x.xx)		

^a Reference group

^b Number of events (incidence per person year at risk)

^c Includes only those categories with at least five total events

10 References

1. Desai M, ter Kuile FO, Nosten F, et al. Epidemiology and burden of malaria in pregnancy. *Lancet Infect Dis* 2007;7:93–104.

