4.4 Randomization and Blinding

(ICH E3; 9.4.3, 9.4.6. ICH E9; 2.3.1, 2.3.2)

Treatment Group Assignments

There will be 5 treatment arms which include both the intervention for the woman during pregnancy and her unborn child(ren) during infancy (Table 1). Non-singleton births from the same mother will be assigned to the same intervention. We will use a 2:1:1:1:1 randomization scheme targeting 100, 50, 50, 50, 50 pregnant women in treatment arms A–E respectively. This randomization scheme will result in a target of 100 women for each of the 3 different treatment arms during pregnancy. A randomization list will be computer generated by a member of the project who will not be directly involved in the conduct of the study. The randomization list will include consecutive treatment numbers with corresponding random treatment assignments. Randomized codes will correspond to the 5 treatment groups using permuted variable sized blocks of 6 and 12 (to account for treatment group A being represented twice as often as the other 4 treatment groups). Sealed copies of the original randomization list and documentation of the procedure used to generate the lists will be stored in the project administrative offices in San Francisco and Kampala. Prior to the onset of the study, a set of sequentially numbered, opaque, sealed envelopes will be prepared. Each envelope will be marked on the outside with the treatment allocation number. The inside of the envelope will contain a piece of paper with the treatment allocation number and treatment group assignment along with a piece of carbon paper.

Table 1. Treatment arms with assignment of study drugs during pregnancy and infancy

Phase of intervention	Treatment arm (target number)				
	A	B	C	D	E
During pregnancy	3 dose SP (100)	3 dose DP (100)		Monthly DP (100)	
During infancy	3 monthly DP (100)	3 monthly DP (50)	Monthly DP (50)	3 monthly DP (50)	Monthly DP (50)

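### Section 9.3 has no rule for a safety row in which one arm has no events: default Poisson output then gives p near 1 and robust GEE gives p near 0 or no standard error

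*SAP*

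**What the plan says.** Section 9.3 sets two methods for Table 13, with 3 dose SP as the reference.

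- **Adverse-event rows:** "We will compare the incidence of various adverse events using Poisson or negative binomial regression models". On reporting it says "We will translate the fitted coefficients and their confidence bounds into percentage effects". It names no likelihood-ratio, exact or penalised method.
- **Vomiting rows:** "We will compare the proportions of study participants with vomiting following each dose of study drugs using generalized estimating equations". The model is log-binomial, and a robust variance is meant to handle several courses in one woman.

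The fallback is for distributional misfit: "Testing for overdispersion in the Poisson regression can detect violations of these assumptions", after which variances may be adjusted or a negative binomial or zero-inflated model used. Nothing covers an arm with no events.

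Footnote c of Table 13 is the only sparse-data rule: "Includes only those categories with at least five total events". It counts events over all arms together. It is attached to the two blocks of individual event types, and not to the vomiting rows, the possibly-related grade 3–4 row or the SAE row.

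Fisher's exact test appears only for proportions in sections 8.2 and 8.3.

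**The concern.** When one of two compared arms has no events, the log rate ratio has no finite estimate. The software stops at a large coefficient, and what it prints next depends on the variance used. A model-based variance explodes. A robust variance is built from residuals, which vanish in the empty arm, so it stays small. One method then understates the evidence and the other invents it.

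Section 9.3 tests a hypothesis about adverse events and tolerability. With about 100 women per arm, an event type seen in only one arm is among the clearest patterns the table could show. If no method is named, the p-value for such a row depends on the package default, or on a choice made after the counts are known.

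**Working it through.** **Inputs.** Arms are equal: "This randomization scheme will result in a target of 100 women for each of the 3 different treatment arms during pregnancy" (section 4.4). The floor is five events in total (Table 13, footnote c). Assumed, because the SAP gives no figures: equal person-time across arms, about 6 drug courses per woman (so 600 per arm), each event in a different woman, and a range of vomiting rates. The SAP states no figure for the safety models, so there is none to reproduce. The sizing figures in Table 5 do not bear on this point.

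**1. Event rows, 0 events in one arm and b in the other.**

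- Exact conditional p = 2 × (1/2)^b.
- Lower 95% limit for the IRR = L/(1 − L), with L = 0.025^(1/b).
- Likelihood-ratio statistic = 2b ln 2 on 1 degree of freedom.
- Wald p is from a Poisson fit with a log follow-up offset.

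| Counts | Wald p | Exact p | Exact lower IRR limit | Likelihood-ratio p |
|---|---|---|---|---|
| 0 v 5 | 0.999 | 0.0625 | 0.92 | 0.008 |
| 0 v 6 | 0.999 | 0.031 | 1.18 | 0.004 |
| 0 v 10 | 0.999 | 0.002 | 2.24 | 0.0002 |

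A second package, fitted to counts of 0/10/10 over the three arms, gave Wald p = 0.991 (standard error 1,554). Its quasi-Poisson fit gave 0.988 and its negative binomial fit 0.994, so those fallbacks do not help. The zero-inflated model was not fitted.

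**2. Vomiting rows, log-binomial GEE with robust errors, 6 courses per woman.**

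- 1 v 0 events: coefficient about −22, robust standard error 1.0, so z is about −22 and p about 1e-107. Fisher's test on women gives p = 1.0.
- 3 v 0 events: coefficient about −23, standard error 0.58, p zero to machine precision. Fisher gives 0.25.

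The coefficient is wherever the iterations stopped, so the p-value has no meaning. When the empty arm is SP, some fits returned no standard error and others p near 0.

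**3. How often an arm is empty.** For n total events and equal rates, P(some arm empty) = 3(2/3)^n − 3(1/3)^n.

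- n = 5: 38%
- n = 6: 26%
- n = 8: 12%
- n = 10: 5%

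The SP arm is empty with probability (2/3)^5 = 13% at n = 5, or (4/5)^5 = 33% if both DP rates are double the SP rate.

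**4. How often the exact verdict would differ.** This needs 0 v 6 or more, in either direction, in a comparison with SP. Summing multinomial probabilities:

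- Equal rates: 0% at n = 5, 0.4% at 6, 2.2% at 8, at most 2.6% (n = 9 or 10).
- Both DP rates doubled: 0% at n = 5, 4.9% at 8, at most 8.7% (n = 11).

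**5. Vomiting.** With rate r per course, P(some arm empty) = 1 − [1 − (1 − r)^600]^3.

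- r = 0.1%: 91%
- r = 0.5%: 14%
- r = 1%: 0.7%

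**The case against.** The strongest reply is that the SAP never specifies Wald inference. A likelihood-ratio test from the planned Poisson fit gives 0.004 for 0 v 6 and 0.0002 for 0 v 10. This stands. A reader might infer that the planned model must report an event type seen only on DP as non-significant. The document does not support that. It leaves the test and interval method open, and the usual default is the one that fails.

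A reader might also take 38% as the rate of missed signals. It is not: it applies at exactly five events, where even 0 v 5 has exact p = 0.0625. What is wrong in those rows is the unbounded interval and meaningless p-value, not an exact-test verdict.

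It would also go too far to say that the safety table is wrong in both directions. Table 13 prints counts for every arm, so 0 v 10 is visible whatever the p-value. Section 6.5.4 gives the DSMB serious adverse events by arm with clinical descriptions. The interim comparison in section 6.5.1 concerns grade 3/4 events and SAEs rather than single sparse categories, and nothing in the SAP suggests that an arm would have none of these. Rows with events in both compared arms do not have this failure.

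What remains is that the methods in section 9.3, run with ordinary defaults, give unusable inference in empty-arm rows, and the five-event floor lets such rows in.

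**Conclusion.** The point holds as a gap in section 9.3 limited to rows where a compared arm has no events. It should be fixed, because the change is small and the output without it is misleading.

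For adverse events the size depends on the count. Empty arms are common just above the floor, but a signal that the exact test would find is lost in at most about 3% of rows under equal rates and about 9% with DP rates doubled. That loss occurs only if Wald output is used.

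For vomiting the p-value is wrong whenever an arm is empty, but this is likely only if vomiting follows well under 1% of courses. The SAP gives no rate from which to judge.

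The results assume equal person-time, one event per affected woman and about six courses each. Repeat events in one woman would weaken the exact p-values: six events among five women give 0.0625 when counted by woman, not 0.031.

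**What to change.** Add to section 9.3, for any Table 13 comparison in which either arm has no events:

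- **Adverse-event rows:** take the p-value and interval from an exact conditional method (split by person-time) or a profile-likelihood method, on the same event counts, so that the row still reports events per person-year. Name one of the two in advance, because they disagree at low counts (0 v 5: exact 0.0625, likelihood ratio 0.008). The exact method is the more cautious choice. Add a note or a woman-level sensitivity check if one woman contributes repeat events.
- **Vomiting rows:** use Fisher's exact test on women with at least one event.
- **All other rows:** keep the planned models.

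State that the rule also covers the rows outside footnote c. Triggering it on a zero count, rather than on a loose threshold for few events, keeps it prespecified and leaves working models alone.

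The cost is a short paragraph and a few lines of code. Exact intervals are somewhat wide, and the few empty-arm vomiting rows would use a woman-level measure while the others remain per course.

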3.2.2. Secondary Outcomes

- **Prevalence of placental parasitemia:** Proportion of placental blood samples positive for parasites by microscopy or LAMP
- **Incidence of maternal malaria:** Episodes of fever and positive blood smear by microscopy

- **Prevalence of adverse birth outcomes:** Proportions of birth outcomes that include congenital malformations, preterm delivery, late spontaneous abortion, LBW (<2500g), stillbirth, or a composite of all of these
- **Incidence of adverse events:** Adverse events stratified by type, severity score and relationship to study drugs
- **Prevalence of anemia:** Proportion of routine hemoglobin measurements < 11 g/dL & < 8 g/dL
- **Prevalence of asymptomatic parasitemia:** Proportion of routine monthly samples positive for parasites by LAMP

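### Table 13 of the SAP counts rare grade 3–4 events and all SAEs by arm in aggregate rows but does not identify them by type

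*SAP*

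**What the plan says.** Section 3.2.2 of the SAP defines the safety outcome as "Adverse events stratified by type, severity score and relationship to study drugs". Section 9.3 refers the final safety results to one skeleton table, Table 13.

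Two blocks of that table list event types by name: "Individual adverse events of any severity ^c" and "Individual grade 3–4 adverse events ^c". Both carry footnote c, which reads "Includes only those categories with at least five total events".

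Three further rows carry no footnote and so have no threshold: "All grade 3–4 adverse events", "Grade 3–4 adverse events possibly related to stud drugs" and "All serious adverse events". Each is shown by arm, with columns for the IRR, its confidence interval and a p-value.

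Three other places bear on the point:
- Section 9.1 has adverse events of every grade recorded, with a separate report form for each grade 3–4 event and each SAE.
- Section 6.5.4 promises short case descriptions, but in the interim reports considered by the DSMB.
- Table 11 (section 8.3) shows congenital anomaly, stillbirth and spontaneous abortion by arm with no minimum count.

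**The concern.** A minimum count is natural for common, mild events, where it keeps the table readable. Here it also governs the severe ones. A named grade 3–4 type with one to four events in the whole trial has no grade 3–4 row. SAEs are not broken down by type at any count.

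Four severe events of one kind in one arm mean something different from four unrelated severe events, and an aggregate row cannot tell these apart. This matters here because section 2.2 presents the trial as the first its authors know of to study DP for malaria prevention in pregnant women, and because the arms are small enough for an uncommon severe reaction to produce only a handful of events.

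**Working it through.** **1. Which rows the threshold reaches.** Footnote c does not say over what the five events are counted. I read it as all three arms combined.

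| Table 13 rows | Footnote c? | A severe type with 1–4 events in total |
|---|---|---|
| Individual types, any severity | yes | row only if milder cases lift the type to five; severe cases are then not separated |
| Individual types, grade 3–4 | yes | no row |
| All grade 3–4 | no | counted by arm, type not named |
| Grade 3–4 possibly related | no | counted by arm if judged related, type not named |
| All SAEs | no | counted by arm if serious, type not named |

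**2. Arm size.** Section 4.4 allocates 300 women 2:1:1:1:1 to arms A–E. The SP arm is 300 × 2/6 = 100. Each DP regimen combines two arms: 300 × (1 + 1)/6 = 100. This reproduces the stated 100 per pregnancy regimen.

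**3. Chance that a one-arm event type occurs but gets no row.** The threshold is a display rule with no calculation behind it, and the SAP gives no adverse-event rates, so the true risk p is an assumption. Take a type that occurs in one arm of 100 only, at most once per woman. The number of events X is then binomial(100, p), and

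P(1 ≤ X ≤ 4) = P(X ≤ 4) − (1 − p)^100.

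| Assumed p | P(X ≤ 4) | P(X = 0) | P(1 ≤ X ≤ 4) |
|---|---|---|---|
| 1% | 0.997 | 0.366 | 0.631 |
| 2% | 0.949 | 0.133 | 0.817 |
| 3% | 0.818 | 0.048 | 0.770 |
| 4% | 0.629 | 0.017 | 0.612 |
| 5% | 0.436 | 0.006 | 0.430 |

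The last column is the relevant one, because with no events there is nothing to identify.

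**4. Strength of the largest unlisted one-arm pattern, 4:0:0.** Two-sided Fisher exact tests:
- 4/100 against 0/100: 2 × C(100,4)/C(200,4) = 2 × 3,921,225/64,684,950 = 0.12.
- 4/100 against the other two arms together, 0/200: C(100,4)/C(300,4) = 3,921,225/330,791,175 = 0.012.

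Given exactly four events and equal rates, the chance that all fall in one arm, whichever it is, is 3 × (1/3)^4 = 0.037. That is for a single event type. With ten independent types of four events each (an assumption), the chance of at least one such split is 1 − (1 − 0.037)^10, about 0.31.

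**The case against.** The strongest reply is that nothing is left out of the count. Every severe event enters its arm's total in the rows without a threshold. One of these is restricted to grade 3–4 events judged possibly related, which is the row closest to a concern about drug reactions. A reader might infer from footnote c that a rare severe event would not be shown at all. Table 13 does not support that reading: the event is shown and its type is not.

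A reader might also see a contradiction with section 3.2.2. Table 13 does use the three axes named there (type, severity, relationship), and a minimum count is a display rule. The fair statement is that the outcome is not fully delivered for rare severe types and for SAEs.

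It is also tempting to say that most serious drug reactions would fall below five events, or that common events would swamp the totals. The SAP gives no rates from which either could be shown.

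Other parts of the reply hold in part. Table 11 covers three important birth outcomes without a threshold. The individual report forms mean that the data will exist. The case descriptions in section 6.5.4 help the DSMB, but they belong to interim reports and do not replace a final display. Table 13 is a skeleton, and a listing may be set out in the protocol or study report, neither of which was available here. The point rests, however, on a rule that the SAP states, not on an absent listing alone.

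Finally, an IRR and p-value from one to four events say little, so a threshold for those columns is sensible. That is a reason to leave the columns blank, not to drop the counts.

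**Conclusion.** The point holds as a minor one. Footnote c removes grade 3–4 types with fewer than five events, SAEs appear only as a total, and the SAP plans no other final display that names them. For a type confined to one arm of 100, the chance that it occurs but gets no grade 3–4 row is above one half at assumed true risks of 1% to 4% (61% to 82%) and 43% at 5%.

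These figures rest on four assumptions: the threshold counts all arms together, the type occurs in one arm only, each woman has at most one event, and 100 women in the arm are followed. If the type also occurs in other arms, the total rises and a row becomes more likely.

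A reader might take the probability of fewer than five events (82% at 3%, 63% at 4%) as the size of the problem, but that includes the case of no events. Nor is a 4:0:0 split evidence of harm in itself: the pairwise p-value is 0.12, and such splits are expected by chance when many types are examined. It is a pattern that a safety reviewer should be able to see. No planned estimate, test or efficacy conclusion is affected.

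**What to change.** Remove footnote c from the block "Individual grade 3–4 adverse events" as a rule on which types are listed. Show the number of events by arm for every grade 3–4 type and every SAE type, either in Table 13 or in an appendix listing to which it refers. Keep the five-event threshold for the any-severity block and as the condition for reporting an IRR, confidence interval and p-value, and state that it counts events over all three arms. The cost is a longer table or an extra listing. Section 9.1 already provides a report form for each of these events, so no new data are needed.
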